6. SCHEDULE OF ACTIVITIES

Refer to STUDY PROCEDURES and ASSESSMENTS sections of the protocol for detailed information on each procedure and assessment required for compliance with the protocol.

Procedure / Assessment	Screening	Baseline	Observation period (6 cycles; 24 weeks) ^j		End of Study ^c
			Weekly ^a	Cycle-base ^b	
Time Window			+ 3 days ^d	+ 7 days ^d	
Informed consent	X				
CRF data					
Patient baseline characteristics; Demography, Height, Weight, Medical history, Prior treatment and surgery history, Primary diagnosis, Site of metastatic and disease, Menopausal status, Treatment being initiated, Line of therapy		X			
ECOG performance status ^k		X	↔X↔		X
Adverse event monitoring (eg, type, grade) ^e			↔X↔		
Treatment (eg, type, duration) ^f			↔X↔		
Palbociclib dosing modification ^g			↔X↔		
Concomitant Medication (Surgery, Radiotherapy)			↔X↔		
Disease progression (if applicable)			↔X↔		
Initial treatment discontinuation (if applicable)			↔X↔		
Study withdrawal (if applicable)			↔X↔		
Study completion					X
PRO data via smartphone-based application					
Patient baseline characteristics; Education, Employment		X ⁱ			
EORTC-QLQ-C30		X ⁱ		X	
PRO-CTCAE ^h		X ⁱ	X		
Overall satisfaction with treatment				X	

PFIZER CONFIDENTIAL

Procedure / Assessment	Screening	Baseline	Observation period (6 cycles; 24 weeks) ^j		End of Study ^c
			Weekly ^a	Cycle-base ^b	
Time Window			+ 3 days ^d	+ 7 days ^d	
Physical activity data via wearable device					
Physical activity		X	↔X↔		

- a. Weekly assessment of PRO-CTCAE will be conducted based on Cycle 1 Day 1 regardless of cycle delay.
- b. Cycle-based assessment of EORTC-QLQ-C30 and Treatment satisfaction will be conducted on Day 15 of each cycle.
- c. End of study is defined as end of 6 cycles of initiated treatment. If patients discontinue the initiated treatment before completion of 6 cycles (eg, due to disease progression) and switch to another treatment, end of study will be end of 24 weeks after initiation of initial treatment. In this case, to assess association between change in QOL and physical activity versus disease progression, data collection [including PROs (EORTC-QLQ-C30 and PRO-CTCAE) and physical activity evaluation, EDC data entry] will continue to the end of the study (ie, 24 weeks after the start of the study) even if the treatment is switched to another treatment.

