- d. Weekly-based assessments will remain open for up to 3 days (72 hours) and cycle-based assessments will remain open for up to 7 days (168 hours).
- e. Safety reporting will follow applicable regulations and is detailed in Section 16.
- f. Type and duration of treatment for advanced breast cancer used during observation period in this study (including endocrine therapy used in combination with palbociclib) will be collected in both group.
- g. Group 1 only.
- h. “Fatigue” and “General pain” are measured as PRO-CTCAE.
- i. Baseline assessment for PRO data will be conducted after obtaining informed consent and before initiating study treatment.
- j. The observation period in this study will be 6 cycles. In Group 1 (palbociclib plus endocrine therapy), palbociclib is administered for 3 consecutive weeks followed by 1 week off treatment to comprise 1 cycle of 4 weeks. If palbociclib is temporarily interrupted (eg, due to adverse event) and the start of the next cycle is delayed, the duration of one cycle may exceed 4 weeks, then, the observation period may exceed 24 weeks. In Group 2 (endocrine monotherapy), 1 cycle is defined as 4 weeks.
- k. To be assessed at Baseline and End of study. If ECOG performance status is assessed during the observation period, the data will be entered into EDC. If patients discontinue the initiated treatment before completion of 6 cycles (eg, due to disease progression) and switch to another treatment, ECOG performance status will be assessed at end of treatment as well.

PFIZER CONFIDENTIAL

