9. RESEARCH METHODS

9.1. Study design

The study is a prospective, multicenter, observational study to evaluate PRO and physical activity using smartphone-based application and wearable device in Japanese patients with HR+/HER2- ABC.

Patients will be enrolled into either palbociclib plus endocrine therapy group (Group 1) or endocrine monotherapy group (Group 2) based on the discretion of the treating physician under routine clinical practice. Total target number of patients is approximately one-hundred in this study (assuming about 20 to 80 patients in each group). The number of enrolled patients will be monitored, and the enrollment will be completed when 100 patients have been enrolled. Of note, the patient who is informed about this study for participation at the time when the number of enrolled patients reaches 100 is allowed to enroll. Enrolled patients will download a smartphone-based application for electronic PRO (ePRO), be provided access to and trained on the use of the application to complete baseline, weekly, and cycle-based assessments for 6 cycles (24 weeks). In addition, enrolled patients will be provided with wearable device and requested to wear the device at all-times, except of while bathing and sleeping, for 6 cycles (24 weeks).

[figure not shown]
In this study, one cycle is defined as follows;

- In Group 1 (palbociclib plus endocrine therapy), palbociclib is administered for 3 consecutive weeks followed by 1 week off treatment to comprise one cycle of 4 weeks. If palbociclib is temporarily interrupted (eg, due to adverse event) and the start of the next cycle is delayed, the duration of one cycle may exceed 4 weeks, then, the observation period may exceed 24 weeks.
- In Group 2 (endocrine monotherapy), one cycle is defined as 4 weeks.

Participation in this study is not intended to change the routine treatment that patients receive as determined by their prescribing clinicians; all treatment decisions and type and timing of disease monitoring are at the discretion of the treating physician. No additional visits to the clinic will be required for the purposes of the study.

Figure 1 summarizes the overall study design.

Figure 1. Study Design

It is anticipated that all data collection for this study will occur over a 24-month period (from the first patient's first visit to the last patient's end of study assessment),

Planned patient enrollment duration: 18 months

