6.2. Secondary Endpoint(s)

6.2.1. EORTC-QLQ-C30 scores

- ✓ The same analysis for other 14 scales of EORTC-QLQ-C30 (5 functional scales [physical, role, emotional, cognitive, and social functioning], 8 symptom scales [fatigue, nausea/vomiting, pain, dyspnea, sleep disturbance, appetite loss, constipation, and diarrhea], and financial difficulties scale) are performed as for global health status.
- ✓ Following analyses of 5 functional scales and Global health status scale of EORTC-QLQ-C30 are performed to assess the associations as follows:

When associations for group 1 and 2 were similar, the group 1 and 2 will be pooled.

- Tabulate patients with and without selected investigator-reported AE at each cycle, summarize the mean values of change in EORTC-QLQ-C30 from baseline at each cycle in each tabulated population, and compare the results at Cycle 1 and Cycle 3 using t-test
- Tabulate patients with and without symptom of PRO-CTCAE at each cycle, summarize the mean values of change in EORTC-QLQ-C30 from baseline at each cycle in each tabulated population, and compare the results at Cycle 1 and Cycle 3 using t-test
- Tabulate patients with disease progression during the observation period, and summarize the mean values of EORTC-QLQ-C30 before and after disease progression

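### The SAP does not require an AE or symptom to precede the Day 15 QLQ-C30 answer it is compared with, so later events can count as exposure

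*SAP*

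**What the plan says.** **Exposure.** SAP 6.2.1 (Protocol 12.5.2 has the same wording) gives two parallel instructions: "Tabulate patients with and without selected investigator-reported AE at each cycle" and "Tabulate patients with and without symptom of PRO-CTCAE at each cycle". Mean change from baseline in the global health status and five functional scales is then summarised for each subset and compared at Cycles 1 and 3 by t-test. SAP 6.2.2 carries a similar analysis to the activity metrics, which SAP 6.1.2.1 averages by week.

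**Outcome timing.** Protocol 6, footnote b: "Cycle-based assessment of EORTC-QLQ-C30 and Treatment satisfaction will be conducted on Day 15 of each cycle". Footnote d keeps the form open for up to 7 days, so answers fall between Day 15 and about Day 22.

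**Cycle length.** Protocol 9.1, Group 1: "palbociclib is administered for 3 consecutive weeks followed by 1 week off treatment to comprise one cycle of 4 weeks", longer if the next cycle is delayed. Group 2: "In Group 2 (endocrine monotherapy), one cycle is defined as 4 weeks".

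**Event timing.** AEs are recorded throughout the active collection period (Protocol 16.2.4.2), not only before Day 15. For symptoms, Protocol 6, footnote a, says: "Weekly assessment of PRO-CTCAE will be conducted based on Cycle 1 Day 1 regardless of cycle delay".

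Neither document says whether the per-cycle status means onset in the cycle, ongoing in the cycle, or present by the time of the questionnaire. Neither says how about four weekly PRO-CTCAE reports become one yes or no.

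**The concern.** The outcome is a score at one time in the middle of the cycle. The exposure, read naturally, is anything that happens in the cycle. A patient whose event starts after she has answered is then placed in the group with the event, although her score was given before it began.

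Two things follow. First, the contrast mixes patients whose event preceded the score with patients whose event followed it. If the latter were no different from unaffected patients when they answered, the difference shrinks. Second, if patients who feel worse on Day 15 are the ones in whom an event is reported later, the contrast partly shows poor quality of life preceding the AE. Protocol 7 states the opposite interest: the impact of treatment and treatment-related AEs on daily life.

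The estimates affected are those for the association of QLQ-C30 and activity with investigator-reported AEs and with patient-reported symptoms. Because the window is undefined, two analysts could also build different tables from the same data.

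**Working it through.** The documents give no effect size, SD, alpha or power for this analysis, and Protocol 12.1 sets the sample size on a practical basis. There is no planned figure to reproduce, so the following is illustration.

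**Inputs from the documents:** completion on day d = 15 or 22; cycle of 28 days; 10 points as the clinically significant change (Protocol 11, SAP 3.1); up to about 80 patients in a group (Protocol 9.1).
**Assumed:** uniform onset of new events; 30% of patients with the AE in the cycle; SD 20 (range 15 to 25); two-sided 5% test. The documents' PALOMA-2 fatigue rates, 39.6% and 28.4%, are not per-cycle rates, so the 30% remains an assumption.

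**Step 1. Share of the cycle after the answer.** f = (28 − d)/28.
- Day 15: 13/28 = 46.4%.
- Day 22: 6/28 = 21.4%.
- In a cycle delayed to 35 days (assumed): 20/35 = 57% and 13/35 = 37%.

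**Step 2. Whole-cycle difference when late events are unrelated to the score.** Let c be the share of affected patients whose event is already ongoing at cycle start and persists to the questionnaire. Observed difference = 10 × [1 − (1 − c)f].

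| c | Day 15 | Day 22 |
|---|---|---|
| 0 | 5.4 | 7.9 |
| 50% | 7.7 | 8.9 |
| 80% | 9.1 | 9.6 |

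**Step 3. If late-event patients already differ when they answer.** Let r be the fraction of the 10-point deficit they already have, with c = 0 and p = 0.30.
- Whole-cycle: 10 × [(1 − f) + f·r].
- Aligned (late-event patients counted as without): 10 × [1 − p·f·r/(1 − p(1 − f))].

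| r | Whole-cycle, Day 15 / Day 22 | Aligned, Day 15 / Day 22 |
|---|---|---|
| 0 | 5.4 / 7.9 | 10 / 10 |
| 0.5 | 7.7 / 8.9 | 9.2 / 9.6 |
| 1 | 10 / 10 | 8.3 / 9.2 |
| 1.5 | 12.3 / 11.1 | 7.5 / 8.7 |

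**Step 4. Power, all events new (c = 0, r = 0).** Whole-cycle status compares 24 with 56 patients (80 × 0.30 = 24) on the diluted difference. Alignment restores 10 points but moves late-event patients to the other group: 24 × (1 − 0.464) ≈ 13 v 67, or 24 × (1 − 0.214) ≈ 19 v 61. Noncentrality = difference/[SD × √(1/n₁ + 1/n₂)]. At SD 20 and Day 15 this is 5.36/4.88 = 1.10 whole-cycle and 10/6.06 = 1.65 aligned. At Day 22 it is 7.86/4.88 = 1.61 and 10/5.25 = 1.90.

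| SD | Day 15: whole-cycle v aligned | Day 22: whole-cycle v aligned |
|---|---|---|
| 15 | 30% v 58% | 56% v 71% |
| 20 | 19% v 37% | 36% v 47% |
| 25 | 14% v 26% | 25% v 32% |

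With 80% of events ongoing at cycle start and SD 20, the figures are about 45% v 50% (Day 15) and 49% v 52% (Day 22).

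**The case against.** The strongest reply is that this is a descriptive tabulation. Protocol 12.1 says the study is not designed for hypothesis testing, Protocol 14 calls it hypothesis-generating and warns about causal attribution, and SAP 5.1 bases no decision on tests. The objectives speak of association only. This limits the consequence. It does not remove the point, because these comparisons are the planned analysis for two named objectives, and an estimate with the wrong time order misleads in a descriptive report too.

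Four stronger readings are tempting and are not supported:

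- **That the plan prescribes whole-cycle status.** It says only that status is tabulated per cycle. Whole-cycle is the natural reading; what can be shown is that the window is undefined.
- **That the bias is certainly toward zero.** This needs late-event patients to be no worse when they answer. Step 3 shows an unchanged contrast at r = 1 and a larger one at r = 1.5.
- **That power falls from 53% to 19%.** The 53% is for 10 points with all 24 patients kept in the affected group. Alignment does not keep them there, so the comparison at Day 15 is 37% with 19%.
- **That a real effect will be declared absent.** No decision rule exists by which it could be.

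Two further parts of the reply stand. Events persisting from earlier cycles are not misclassified, so Cycle 3 may be less affected than Cycle 1. The onset model also does not describe PRO-CTCAE, which is a repeated weekly status. There the gap is the missing weekly-to-cycle rule, and in Group 1 the weekly reports can drift against delayed cycles.

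**Conclusion.** The point holds in limited form. The questionnaire comes in mid-cycle, events are collected across the cycle, and no rule puts the event before the answer. If late events are unrelated to the earlier score, a true 10 points would appear as 5.4 to 7.9 with all events new and uniform onset, 7.7 to 8.9 with half ongoing at cycle start, and 9.1 to 9.6 with 80% ongoing. Dilution is the expected direction but not a certain one, and its size cannot be fixed from the documents because they give neither onset patterns nor carry-over. The power figures rest on an assumed SD and AE share and are illustrative. The primary endpoints are untouched. This should be corrected because it is cheap and affects two secondary objectives; it does not threaten the study.

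**What to change.** In SAP 6.2.1, for each cycle's comparison:

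- **AE status:** with the AE if it is ongoing at the actual QLQ-C30 completion date, or started in that cycle on or before that date. Events starting later do not count for that cycle.
- **PRO-CTCAE status:** the last weekly report on or before the completion date, with a stated threshold for having the symptom.
- **Activity metrics (SAP 6.2.2):** name the week whose average represents each cycle, and take AE or symptom status in that same week.
- **Sensitivity analysis:** repeat with whole-cycle status, so that the effect of the window can be seen.

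The cost is SAP wording, slightly more programming and somewhat fewer patients in the affected group (about 13 or 19 in place of 24 in the illustration). The AE rule still counts an event that began and resolved within the cycle before the answer, and under Step 3 the aligned contrast is itself below 10 when late-event patients already feel worse. No new data collection appears necessary: SAP 6.6 already plans to describe AE timing, and the ePRO forms open and close in timed windows. The documents do not expressly list AE onset dates or questionnaire time stamps, so the sponsor should confirm that both are in the analysis data.

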12.5.2. Secondary endpoints

Analysis of EORTC-QLQ-C30 scores

- The same analysis for other 14 scales of EORTC-QLQ-C30 (5 functional scales [physical, role, emotional, cognitive, and social functioning], 8 symptom scales [fatigue, nausea/vomiting, pain, dyspnea, sleep disturbance, appetite loss, constipation, and diarrhea], and financial difficulties scale) are performed as for global health status.

- Following analyses of 5 functional scales and Global health status scale of EORTC-QLQ-C30 are performed to assess the associations as follows:
 - ✓ Tabulate patients with and without selected investigator-reported AE at each cycle, summarize the mean values of change in EORTC-QLQ-C30 from baseline at each cycle in each tabulated population, and compare the results at Cycle 1 and Cycle 3 using t-test
 - ✓ Tabulate patients with and without symptom of PRO-CTCAE at each cycle, summarize the mean values of change in EORTC-QLQ-C30 from baseline at each cycle in each tabulated population, and compare the results at Cycle 1 and Cycle 3 using t-test
 - ✓ Tabulate patients with disease progression during the observation period, and summarize the mean values of EORTC-QLQ-C30 before and after disease progression

Analysis of physical activity metrics

- The same analysis for other physical activity metrics (eg, steps) is performed as for Sedentary time.
- The similar analyses of each physical activity metrics, as same as that for EORTC-QLQ-C30, are performed to assess the associations.

Association between EORTC-QLQ-C30 and Physical activity

- The Pearson's correlations between change in PRO and physical activity metrics will be calculated at each measurement time point.

Patient satisfaction

- Patient satisfaction will be summarized descriptively through tabular displays of mean, median, ranges and standard deviations of continuous variables and frequency distributions of categorical variables, by measured points.

Adverse events and PRO-CTCAE

- Investigator-reported AE and patient-reported AE will be summarized.
- Association between investigator-reported AE and patient-reported AE will be assessed using contingency table and weighted Kappa coefficient.

Feasibility of the measures

- The number of responses from EORTC-QLQ-C30 and the number of physical activity data are summarized at each measurement point

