5.2. General Methods

All endpoints will be summarized by descriptive statistics.

As a secondary analysis, we will perform t-test or nonparametric test (if needed) to assess the association between primary endpoints and adverse events and disease progression. **CC1**
[REDACTED]

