6.1. Primary Endpoint(s)

6.1.1. Change in “EORTC-QLQ-C30 (Global health status scale)”

6.1.1.1. Main Analysis

As primary analysis of EORTC-QLQ-C30, change in “Global health status scale” from baseline is summarized at each measurement time point, separately by groups. Baseline values are those measured between enrollment and the day before treatment start.

For patients who could not be measured before treatment start, the values measured within 6 days of the treatment start is treated as the baseline value.

Least squared mean and the 95% CI of the score for each cycle will be estimated using mixed effect model for repeated measures. The covariates included in the model will be group, cycle (categorical variable), group -and-cycle interaction term, and baseline score.

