6.2.2. Physical activity metrics

- ✓ The same analysis for other physical activity metrics (steps, MVPA time) is performed as for Sedentary time.
- ✓ The similar analyses of each physical activity metrics, as same as that for EORTC-QLQ-C30, are performed to assess the associations.

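### The AE and symptom comparisons rest on unadjusted change scores alone; a baseline-adjusted difference should be reported beside them

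*SAP*

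**What the plan says.** Protocol 12.5.2 sets up the comparison: "Tabulate patients with and without selected investigator-reported AE at each cycle", and likewise for PRO-CTCAE symptoms. SAP 6.2.1 repeats it for the five functional scales and global health status. The summary it asks for is to "summarize the mean values of change in EORTC-QLQ-C30 from baseline at each cycle in each tabulated population". The test that goes with this summary is worded as follows: "compare the results at Cycle 1 and Cycle 3 using t-test". SAP 6.2.2 extends it to activity: "The similar analyses of each physical activity metrics, as same as that for EORTC-QLQ-C30, are performed to assess the associations". The general rule in SAP 5.2 is "we will perform t-test or nonparametric test (if needed) to assess the association between primary endpoints and adverse events and disease progression". None of this visible text names a covariate.

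The main analyses of the same outcomes are handled differently. For global health status, SAP 6.1.1.1 states: "The covariates included in the model will be group, cycle (categorical variable), group -and-cycle interaction term, and baseline score". The sedentary-time model in SAP 6.1.2.1 also includes baseline. The covariate is therefore at hand. Protocol section 6 says of it: "Baseline assessment for PRO data will be conducted after obtaining informed consent and before initiating study treatment"; SAP 6.1.1.1 adds a fallback for patients not measured in time.

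**The concern.** Patients with and without an AE or symptom are not randomised, and the subsets are formed after treatment starts. SAP 6.2.1 does not require a symptom to be new since baseline, so patients already in pain or fatigued at entry can fall in the symptomatic subset. The two subsets may well start at different levels.

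Subtracting baseline removes such a difference fully only if it would have persisted unchanged. If scores drift back towards a common mean, part of the contrast in change comes from the starting levels and not from the AE. Separately, a change score carries the measurement noise of both visits, so its interval is wider than a model with baseline as covariate would give. At stake are the secondary objectives on the association of AEs and symptoms with quality of life and activity, in a study where one treatment group may be small ("assuming about 20 to 80 patients in each group").

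**Working it through.** **Nothing to reproduce.** The documents give no alpha, power or precision for these t-tests, and protocol 12.1 sets the sample size of 100 on practical grounds.

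**Inputs.** From the documents: up to 80 patients in a group (protocol 9.1); fatigue in 39.6% and 44.1% of palbociclib patients in the two phase 3 trials (protocol section 7), taken as a 40% AE share, so 48 without and 32 with; 10 points as the clinically significant change (protocol section 11), used here as a between-subset difference. Assumed: SD 20 at both visits; correlation rho between baseline and on-treatment score of 0.3, 0.5 or 0.7; two-sided 5% tests; a 10-point baseline difference. The t-test is read as with versus without at each of Cycles 1 and 3.

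**Precision, balanced baselines.** Change-score variance is 2·SD²·(1−rho). Baseline-adjusted variance is SD²·(1−rho²). The ratio is (1+rho)/2. For the standard error of the difference, multiply the variance by 1/48 + 1/32 = 0.0521 and take the square root.

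| rho | Variance, change / adjusted | Ratio | SE, change / adjusted | 95% CI half-width | Power for 10 points |
|---|---|---|---|---|---|
| 0.3 | 560 / 364 | 0.65 | 5.40 / 4.35 | 10.6 / 8.5 | 46% / 63% |
| 0.5 | 400 / 300 | 0.75 | 4.56 / 3.95 | 8.9 / 7.7 | 59% / 72% |
| 0.7 | 240 / 204 | 0.85 | 3.54 / 3.26 | 6.9 / 6.4 | 81% / 87% |

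The ratio does not depend on the SD. For a group of 20 with a 30% share (14 versus 6), the half-widths go from 22.6 to 18.2, 19.1 to 16.6 and 14.8 to 13.7 points, so neither method resolves 10 points there.

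**Precision, 10-point imbalance.** In simulation (3,000 runs per setting, 48 versus 32) the SE falls from 5.42 to 4.53, 4.59 to 4.09 and 3.61 to 3.45. That is about 16%, 11% and 4% smaller, against 19%, 13% and 8% with balanced baselines.

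**Which estimate is off.** Let d be the baseline difference (with minus without) and b the slope of follow-up on baseline; with equal SDs, b = rho. In any data set the unadjusted minus the adjusted difference equals (b−1)·d, using the fitted slope and the observed d. For d = −10 this is (0.3−1)·(−10) = +7, then +5 and +3 for slopes 0.5 and 0.7. The arithmetic does not say which estimate is right. Two models with no AE effect give opposite answers:

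| rho | (a) Regression to a common mean: unadjusted / adjusted estimate | Rejections | (b) Stable difference: unadjusted / adjusted estimate | Rejections |
|---|---|---|---|---|
| 0.3 | +7.1 / +0.1 | 26% / 5% | −0.1 / −7.2 | 6% / 36% |
| 0.5 | +5.0 / +0.1 | 19% / 4% | 0.0 / −5.0 | 5% / 22% |
| 0.7 | +3.1 / +0.1 | 14% / 6% | +0.1 / −2.9 | 5% / 14% |

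If the AE truly costs 10 points, the unadjusted difference under (a) is about −3, −5 and −7, with the adjusted one near −10. Under (b) the unadjusted difference stays near −10, while the adjusted one overstates harm at about −17, −15 and −13.

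**The case against.** The strongest reply is that for non-randomised subsets neither change scores nor baseline adjustment is right in general (Lord's paradox). A reader might infer that the planned t-tests are biased and should be replaced by a baseline-adjusted model. The documents do not support that. They give no slope and no baseline difference, and a stable difference is quite plausible when the split is on having a symptom and not on developing one. In that case the replacement would bring in an error of the same size in the other direction. This part of the reply stands in full.

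Two other tempting readings also fail. Baseline is not ignored, because it is subtracted. Nor would imbalance simply pass for AE harm: if AE patients start worse, the artefact hides or reverses harm, and it mimics harm only if they start better.

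It can also be said that the objective is an association, that protocol section 14 calls the study hypothesis-generating, and that SAP 5.1 plans no decisions about the drugs from tests. This limits the weight of the point, but does not explain why the SAP adjusts for baseline in one analysis of these outcomes and not in the other.

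SAP 6.4 lists fatigue as a subset variable for the primary endpoints, whose models include baseline, but it specifies no adjusted contrast between patients with and without fatigue. Redacted text after the association sentence in SAP 5.2, and elsewhere, might hold adjusted analyses. That cannot be checked, and the visible rules in 6.2.1 and 6.2.2 stand as written.

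**Conclusion.** The point holds in a limited form. That baseline is not used as a covariate in these comparisons is plain from the visible text. The precision loss follows for any correlation below 1 with equal SDs: an adjusted variance of 0.65 to 0.85 of the unadjusted one over the assumed range, with a smaller gain under imbalance.

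The bias is conditional. It arises if the subsets start at different levels and scores regress to a common mean, and its size then is (slope−1) times the baseline difference. A 5-point difference would give half the figures shown for 10 points. All slopes, SDs and baseline differences used here are assumptions. What the plan lacks is any way for a reader to see whether a reported association depends on where the subsets started.

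**What to change.** In SAP 6.2.1 and 6.2.2, and in protocol 12.5.2 to match:

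- Keep the unadjusted mean change by subset.
- Report the baseline value of each scale or metric by subset.
- Add a linear model of change on AE or symptom status plus the baseline value of that same scale or metric.
- Give both differences with 95% CIs at Cycles 1 and 3.
- State what each assumes: a stable difference between subsets for the unadjusted one, and a common regression line on baseline for the adjusted one.
- Treat a conclusion as robust only if the two agree.

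This takes a few sentences of text and no new data, since baseline is already needed to compute change. The cost is slightly more analysis and two estimates to interpret in a secondary, exploratory comparison.
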